## 1. BACKGROUND AND RATIONALE

Systemic lupus erythematosus (SLE or lupus) is a complex and severe rheumatic disease with exceedingly diverse clinical manifestations, including renal manifestations. Renal involvement is a frequent aspect of SLE, as 40–75% of SLE patients develop lupus nephritis (LN), most often within five years of the disease onset (1), although some patients do develop this complication later (2).

The risk of developing LN is higher among men, young people, and people of non-European ancestry (3). This risk varies significantly between different regions of the world and different races and ethnicities. For example, black and Hispanic SLE patients develop LN earlier, and have worse outcomes than white patients with SLE, including death and end-stage renal disease (ESRD) (4). As for Arab SLE patients, LN seems to be common and occurring in 37–69% of SLE patients in the Arab dominated groups, particularly among those from Saudi Arabia, and in 50% of the exclusively Arab group (1). Also, LN is more common in patients with anti-dsDNA and it is less frequent in those with positivity for rheumatoid factor and discoid manifestations (2).

LN is recognised as a major cause of morbidity, mortality, health expenditure, and impaired quality of life (QoL) in patients with SLE (1). However, an early diagnosis and treatment are associated with a better prognosis (2). In many patients, LN ends in chronic kidney disease or ESRD despite potent anti-inflammatory and immunosuppressive therapies (4). Also, patients with LN have a higher standardised mortality ratio (6–6.8 versus 2.4) and die earlier than SLE patients without LN (4). Importantly, 10-year survival improves from 46% to 95% if disease remission can be achieved (4). Despite the improvements in care, LN patients often suffer long-term morbidity that can adversely affect their QoL and ability to work (5), resulting in substantial direct and indirect costs. Patients with flares incur higher direct and indirect costs as compared to those without flares. Flares in major organs such as kidneys increase disease costs much more than other organ flares. The high costs associated with LN flare may be reduced by treatments that effectively control disease activity and prevent major organ flares (6,7). Thus, due to both direct and indirect costs, LN leads to a very high burden of disease. Improvement in disease activity and physical health, and prevention of organ damage, may reduce direct and indirect costs in SLE and LN (6,7,8,9,10,11).

LN can be asymptomatic or “silent” (detected by routine renal biopsy), or presenting with trace proteinuria or active urinary sediments (microscopic haematuria, pyuria or cellular casts), or with serious proteinuria (nephrotic syndrome) and acute nephritic syndrome with rapid progression to acute renal failure (5). LN evaluation consists of assessing serum creatinine level, urine dipstick testing, and urine sediment examination (3). Many patients will have findings suggestive of LN at the initial diagnosis of SLE, and patients with SLE should undergo screening for LN at diagnosis, at least yearly thereafter, and any time there is concern for a lupus flare (3). Furthermore, renal biopsy is the gold standard diagnosis and histological classification of LN (3,5). A complete staining pattern for LN consists of finding positive staining for immunoglobulin (Ig) G, A, and M with C1q, C3, and C4 (5). Moreover, patients with LN that is refractory to treatment should be evaluated for other possible causes for the persistence of proteinuria or deterioration in renal function. These include the nephrotoxic side effects of medications (such as the calcineurin inhibitors and nonsteroidal anti-inflammatory drugs [NSAIDs]), renal vein thrombosis, infections, over diuresis, and poorly controlled hypertension. Treatment compliance

should be checked. To help guide further treatment decisions, a repeat renal biopsy should be considered in patients with persistently active serological markers (5,12). Indeed, a second biopsy provides information on: 1) the histological transformation of LN classes; 2) the degree of residual activity in the kidneys; and 3) the extent of chronic irreversible changes and their progression since the initiation of immunosuppressive treatment (5).

To help physicians in diagnosis and care management, new guidelines and recommendations for the management of LN have been proposed by the European League Against Rheumatism (EULAR) and European Renal Association-European Dialysis and Transplant Association (ERA-EDTA) in 2020 (12). Beside the EULAR recommendations, other parameters may be considered such as: patient education, coexisting morbidities, fibromyalgia, stress reduction, and many organ specific complications and aspects of SLE (e.g. autoimmune haemolytic anaemia, and screening for pulmonary hypertension) (13). Patients are usually followed up by rheumatologists and nephrologists in hospital-based physicians in specialised SLE centres (14).

As for the treatment of LN, it depends on disease severity and risk for progressive kidney damage (3). A conservative treatment is used for the non-proliferative forms of LN (class II and V with sub-nephrotic range proteinuria and normal glomerular filtration rate), with treatment focused on blood pressure control with renin-angiotensin system blockade and immunomodulation with antimalarials (e.g. hydroxychloroquine) (3). As for immunosuppressive agents, these are used as needed to treat extrarenal manifestations only. In addition to antimalarials and renin-angiotensin system blockade, proliferative forms of LN (class III, IV, or III/IV+V) and class V with nephrotic syndrome are treated with systemic immunosuppression combined with high-dose corticosteroids to suppress inflammation and control autoimmunity (3). This induction phase of treatment generally lasts 3–6 months and is followed by a prolonged, but less intense maintenance phase, often lasting years. It is not clear when maintenance therapy can be withdrawn. A repeat kidney biopsy showing histologic remission during maintenance in LN patients who have achieved complete clinical remission, or who have stable but persistent proteinuria, may help in making a decision to taper off therapy (4). During the maintenance phase, immunosuppressive/cytotoxic agents are continued but de-escalated slowly over time to limit risk for LN flares. Biological drugs developed more recently show interesting beneficial effects in LN (4). They decrease the level of B lymphocytes which contributes to the decrease in autoantibodies known to play the central role in disease activity and consequently decrease the global inflammation level (15).

There is a paucity of data in the Gulf countries on LN care management (treatment strategies, healthcare pathways, healthcare resource utilisation [HCRU] and costs), especially in moderate and severe cases. In this context, GSK has decided to carry out an observational study mainly to characterise LN patients in 5 Gulf countries who may benefit from early intervention. Also, in order to have an accurate estimation of the costs of LN care management. This study aims at evaluating disease costs according to patients' profile.

## 1.1. Rationale

SLE is a potentially serious, chronic, autoimmune disease, which can affect multiple organs of the body, including the kidneys (LN). The high variability and its unpredictable course (flaring/remission), combined with a lack of indicated and integrated treatments, induce a high

unmet need within the patient population. Reliable data on SLE- and LN-related care patterns and resource utilisation in the Gulf region are currently unavailable.

The expected key outcomes of this study will be:

- Description of clinical characteristics, demographics, treatment and health-related quality of life (HRQoL) of LN patients.
- Description of “real-world” standard of care and HCRU associated with LN in the Gulf region.

The information collected may be used for scientific interactions with HCP's and payers and for developing a scientific communication plan for Gulf. It can also be used for clinical research, for health planners, for clinical management and education/information for patients/ healthcare professionals/ payers, etc. The study protocol is designed to obtain an accurate, “real-life” picture of LN patients in the Gulf countries.

## **2. OBJECTIVES**

### **2.1. Primary Objective**

Describe patient profile, demographic features, clinical manifestations, comorbidities, severity, treatments and HRQoL of LN patients over one-year period across 5 Gulf countries (UAE, Qatar, Bahrain, Kuwait and Oman).

### **2.2. Secondary Objectives**

1. Describe refractory LN cases, involving rituximab, and to assess changes in serological markers of disease activity (including anti-nuclear antibody, anti-dsDNA antibody and complement levels) over the treatment period.
2. Assess the association between clinical factors, biomarkers, treatment and renal remission.
3. Assess impact of LN on HRQoL over a one-year period after diagnosis or enrolment.
4. Describe LN HCRU and direct medical cost, associated with LN management across 5 Gulf countries over a one-year period.
5. Exploring the difference in treatment patterns by physician profile (physicians in private versus public hospitals).

### 3. RESEARCH METHODOLOGY

#### 3.1. Study Design

The LUNELORD study is a multicentre prospective study compromising of a patient-completed survey and retrospective chart review ([Figure 1](#)).

This study will enrol approximately 200 patients with clinician diagnosed LN cases from 5 different countries in the Gulf (UAE, Bahrain, Qatar, Kuwait and Oman). Enrolment is planned to last for 6 months from June 2021 till November 2021.

[figure not shown]
Each site is planned to enrol around 16 patients, with the aim to have around 50% of the patients with renal remission and 50% with no renal remission to ensure the study meets the sample size and power assumptions provided below. The recruitment will not be competitive among participating sites for optimal representation of the study population. Since rheumatologists usually play a leading role in the disease management in multidisciplinary setting, clinical sites will predominantly be selected from this clinical specialty. Treatment of flares/ exacerbations/ organ manifestations, recommended by other specialists than rheumatologists / immunologists (for example nephrologists), will be considered and registered during the study by the investigators.

Centres from the private and public sectors will be chosen based on their ability to fulfil the objectives of the study and the ability to enter data onto the electronic case report form (eCRF). The country regulation will not impact the selection criteria of the centre or patient recruitment; major sites in each participating country will be selected and are representative of most patients. All nationalities have also been included as well. Given the ethnic diversity of the region study investigators will ensure to include all ethnicities. Prior to the selection of the sites, feasibility of study in all clinical sites and pilot eCRF will be tested and trainings will be conducted.

GSK study team will choose sites, representing major lupus treatment centres in respective countries, based on availability of sufficient potentially eligible patient population, their competency and experience to conduct research, their ability to fulfil the objectives of the study, ability to enter the data onto the eCRF. Prior to selection feasibility all clinical sites and pilot eCRF will be tested and trainings will be conducted.

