### 3.3.2. Sample Size / Power Calculations

As other similar research recruited a sample size ranging between 200 and 300 patients (18,19) the decision was made to proceed with 200 sample size in this research. This sample size would provide a significant power to interpret the results of the study. In addition, due to overall budget

constraints the maximum number of participants allocated for the study has been determined as 200.

Based on the sample size determination using Slovin's formula and assuming the total SLE population in Gulf countries is 5,600 patients, while 40% of SLE patients manifest with lupus nephritis (LN), the entire LN population size was estimated as 2,240 patients disease onset ([1](#)).

The margin of error (significance level), denoting the allowed probability of committing an error in selecting a small representative of the population, is 0.067 for the 93% of confidence that the data are going to be reflective of the entire LN population, given the assumptions of 200 LN patients, required to achieve this significance level ([20](#)).

Significance of the adverse factors, impacting the data accuracy and completeness, will be assessed during the data acquisition and may result in respective adjustments to the sample size.

In addition, taking into account our secondary hypothesis on the association between clinical factors, biomarkers, treatment and renal remission, a sample size of 200 observations (of which 65% are in not in renal remission=0 and 35% are in renal remission=1) achieves 80% power at a 0.050 significance level to detect a change in Prob(Y=1) from the baseline value of 0.200 to 0.385 ([Table 1](#)). This change corresponds to an odds ratio of 2.508.

**Table 1.** Tests for the odds ratio in logistic regression with one binary X and other Xs  
(Wald Test) (21)**Numeric Results**

Power	N	Pcnt N X=1	P0	P1	Odds Ratio	R Squared	Alpha	Beta
0.80000	200	35	0.200	0.385	2.508	0.000	0.050	0.20000
0.80000	200	35	0.200	0.409	2.770	0.200	0.050	0.20000
0.80000	200	35	0.200	0.444	3.199	0.400	0.050	0.20000
0.80000	200	35	0.200	0.504	4.065	0.600	0.050	0.20000
0.80000	200	35	0.200	0.643	7.200	0.800	0.050	0.20000
0.90000	200	35	0.200	0.418	2.871	0.000	0.050	0.10000
0.90000	200	35	0.200	0.446	3.216	0.200	0.050	0.10000
0.90000	200	35	0.200	0.487	3.791	0.400	0.050	0.10000
0.90000	200	35	0.200	0.555	4.985	0.600	0.050	0.10000

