4.5. Specific Analyses

4.5.1. Analysis of the primary objective

Patient demographics will be summarised using the methods presented in the general consideration section (see Table 1). Similar analysis will be done for the clinical manifestations, comorbidities, severity, treatments and HRQoL of LN patients over one year (Tables 2-5).

4.5.2. Analysis of secondary objective 1

Summary statistics will be used to describe refractory LN cases and the independent t-test or Wilcoxon signed rank test along with repeated measures analysis will be used to test for changes in serological markers of disease activity at one year and over the treatment period. Changes in categorical variables at one-year period will be tested using the McNemar's test (see Table 6).

4.5.3. Analysis of secondary objective 2

Univariate and multivariate logistic regression with renal remission as the dependent variable and clinical factors and treatment as the independent variables. Odds ratios and 95% confidence intervals (CIs) will be presented. Variables with a p-value of 0.25 or less along with known associated factors with renal remission will be used to build the final multivariate model. The final multivariable model will contain only significant factors or those who have confounding effect on others in the model.(see Table 7).

4.5.4. Analysis of secondary objective 3

Changes in SF-36 total score from baseline to one year will be test for significance using the paired t-test (or Wilcoxon signed rank test for non-normal distribution. The same analysis will be done for all subscales of the SF-36 (see Table 8).

4.5.5. Analysis of secondary objective 4

For each country, the average HCRU and direct medical cost will be estimated along with its 95%CI (see Table 9).

4.5.6. Analysis of secondary objective 5

CCI

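### No visible analysis or precision statement accounts for site, although about 200 patients at about 16 per site implies roughly 12–13 sites

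*Protocol*

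**What the plan says.** Protocol 3.1 sets the scale: "This study will enrol approximately 200 patients with clinician diagnosed LN cases from 5 different countries in the Gulf". On recruitment by centre it says: "Each site is planned to enrol around 16 patients". The number of sites is not given. The same sentence adds a target for the remission mix: "with the aim to have around 50% of the patients with renal remission and 50% with no renal remission". It is unclear whether this balance is meant within each site or overall; Protocol 3.3 words it for the study population as a whole.

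The visible analyses are these:
- **Change from baseline to 12 months (SAP 4.1):** paired t-test, Wilcoxon signed rank, McNemar and repeated measures.
- **Objective 2 (SAP 4.5.3):** "Univariate and multivariate logistic regression with renal remission as the dependent variable".
- **Objective 4 (SAP 4.5.5):** for each country, "the average HCRU and direct medical cost will be estimated along with its 95%CI". SAP Table 9 adds a cost row pooled over countries, also with a 95% CI.
- **Cost drivers (Protocol 4.5):** multiple linear regression. Model details are left to the SAP, whose visible text does not return to them.
- **Objective 5, private versus public (Protocol 2.2 and 4.7):** exploratory, with no test named. SAP 2.2.5 and 4.5.6 are redacted.

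On precision, Protocol 3.3.2 says that 200 patients "achieves 80% power at a 0.050 significance level to detect a change in Prob(Y=1) from the baseline value of 0.200 to 0.385". The matching effect size is given next, in a sentence of its own: "This change corresponds to an odds ratio of 2.508". Protocol 3.3.2 and SAP 3.2 both give a margin of error of 0.067 for a population of 2,240. Nowhere in the visible text is there an ICC, a design effect, a site term, GEE or cluster-robust errors.

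**The concern.** The plan itself gives reasons to expect patients at one site to be alike. Renal remission may rest on the physician's discretion (Protocol 3.2.2). Prices are taken by country or institution (Protocol 3.1.6). The physician survey exists partly to record treatment patterns at site level (Protocol 3.1.5), and its form asks which activity indices and laboratory tests each physician uses (Appendix 5).

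Where outcomes cluster by site, formulas that treat patients as independent give standard errors that are too small for means, for proportions and for any factor that is constant within a site. Private versus public is such a factor, because Protocol 3.1 selects centres from the two sectors. The repeated-measures analysis deals with correlation within a patient, not within a site.

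The study also aims beyond its own centres: Protocol 3.1 calls the chosen sites representative of most patients, and 3.3.2 extends the result to the whole LN population of the region. Between-site variation therefore belongs in the uncertainty.

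**Working it through.** **Inputs.** N = 200 and m = 16 per site (Protocol 3.1); five countries; P0 = 0.200, P1 = 0.385, two-sided alpha 0.05, 35% with X = 1 (Protocol 3.3.2 and Table 1); LN population 2,240. The ICC is an assumption, shown from 0.01 to 0.10.

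**1. The plan's own figures.** The formula for logistic regression with one binary X is N = [1.96·√(P(1−P)/B) + 0.842·√(P0(1−P0) + P1(1−P1)(1−B)/B)]² / [(P0−P1)²(1−B)]. With B = 0.35, P = 0.65×0.200 + 0.35×0.385 = 0.265. This gives N = 200.8, and power of 0.7985 at N = 200. Slovin's formula gives 2,240/(1 + 2,240×0.067²) = 202.6, or e = 0.0675 at n = 200. Both figures reproduce, and both assume independent patients.

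**2. Clusters.** 200/16 = 12.5 sites. Per country, on average, 200/5 = 40 patients and 12.5/5 = 2.5 sites.

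**3. Design effect for means, proportions and site-level factors.** DE = 1 + 15×ICC. Effective n = 200/DE. Half-width for a 50% proportion = 1.96·√(0.25·DE/200). Actual coverage of a nominal 95% interval = 2Φ(1.96/√DE) − 1.

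| ICC (assumed) | DE | Effective n | SE multiplier | Half-width, points | Actual coverage |
|---|---|---|---|---|---|
| 0 | 1.00 | 200 | 1.00 | 6.9 | 95% |
| 0.01 | 1.15 | 174 | 1.07 | 7.4 | 93% |
| 0.02 | 1.30 | 154 | 1.14 | 7.9 | 91% |
| 0.05 | 1.75 | 114 | 1.32 | 9.2 | 86% |
| 0.10 | 2.50 | 80 | 1.58 | 11.0 | 78% |

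Read as a half-width, the stated 0.067 becomes 0.067×1.07 = 0.072 at ICC 0.01 and 0.067×1.58 = 0.106 at ICC 0.10.

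**4. Type I error of an unadjusted 5% test.** This was simulated with 13 sites of 16, outcome prevalence 35% and 8,000 runs per cell, for outcome ICC 0.02 / 0.05 / 0.10:
- Exposure fixed by site (4 of 13 sites exposed): 8.6% / 13.6% / 21.5%.
- Patient-level exposure that does not vary by site: 5.0% / 5.1% / 5.3%.
- Patient-level exposure with its own site ICC of 0.10: 5.0% / 5.2% / 6.2%.
- Patient-level exposure with its own site ICC of 0.20: 5.4% / 5.9% / 8.6%.
- Remission fixed at 8 of 16 in every site, exposure ICC 0.10: about 4%.

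As a check, the approximate design effect for a patient-level coefficient is 1 + 15×ICC(exposure)×ICC(outcome). With 0.20 and 0.10 this is 1.30, and 2[1 − Φ(1.96/√1.30)] = 8.6%, which agrees with the simulation.

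**5. Per-country cost intervals.** With two or three sites, a site-adjusted mean has 1 or 2 degrees of freedom and a t multiplier of 12.7 or 4.3.

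**The case against.** The study is mainly descriptive. SAP Tables 1–6 give counts, means, SDs and quartiles; 95% CIs are planned only for odds ratios and for HCRU and cost. That stands: a reader might infer from the table above that planned intervals for proportions under-cover, but none is planned. For proportions the point applies only to the 0.067 margin and to any interval added later.

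A reader might also infer that power for the odds ratio of 2.508 collapses. At the effective n above it would fall from 0.80 to 0.74, 0.69, 0.57 and 0.43 for ICC 0.01, 0.02, 0.05 and 0.10, but only for a factor fixed by site. Objective 2 names disease activity, biomarkers and treatment, and SAP Table 7 shows age, gender, treatment and SLEDAI-2K, all recorded per patient. There the loss is small, and the test is slightly conservative if the 50/50 remission aim is met within each site.

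Paired tests cancel stable site differences, so what matters there is the ICC of the change scores, which is unknown. Country cost intervals are already split by country and rest on about 40 patients each, so between-country price differences do not enter them.

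Protocol section 5 concedes feasibility-based site selection, caution in extrapolation and poor precision in small countries. It does not mention correlation within sites, so it only partly answers the point.

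**Conclusion.** The point holds as an omission of moderate weight: nothing visible in the analysis or precision statements accounts for site. Its full size, a design effect of 1.15–2.50, applies to the pooled mean cost in SAP Table 9, to the 0.067 margin, to site-level terms in the cost-driver regression and to any private-versus-public contrast tested on patients. The pooled cost row is the most exposed planned interval, because prices also differ by country and institution. Patient-level terms in the cost-driver regression are affected less, in proportion to how far the predictor itself clusters by site.

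For the renal-remission model the matter is less one of error rates than of confounding. If prescribing and the discretionary remission call both vary by site, a treatment odds ratio without a site term mixes the two.

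It is tempting to say that every planned analysis ignores site and that private versus public is the worst case of understated error. The documents do not support that: the SAP text for objective 5 is redacted and the protocol states no test or error for it. What can be said is that its information comes from about 12–13 sites.

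The sizes rest on an assumed ICC, equal site sizes of 16 and a derived number of sites.

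**What to change.** In SAP 4.1 and 4.5:
- Fit the renal-remission logistic model and the pooled cost models with a random intercept for site, or GEE with a small-sample correction for 12–13 clusters, and with country as a fixed effect. Report the ICC.
- Give a cluster-adjusted CI for the pooled mean cost.
- Keep the per-country cost CIs but label them as conditional on the sampled sites. With 2–3 sites per country on average, a site-adjusted interval would be nearly uninformative.
- State in the sample-size section that the 0.067 margin and the Table 1 power assume independent patients.
- Make site the unit of inference for any private-versus-public comparison, unless the redacted text already does so.

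No extra patients or visits are needed, which matters because enrolment is capped at 200. The models need only the site identifier for each patient. The price is somewhat wider intervals and slightly more analysis work.
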